8.3 Follow-up visits

Female participants will be asked to return for follow up at 2, 4 and 6 months after enrollment. They will be instructed to return on the scheduled day regardless of their menstrual cycle. At each woman’s follow-up visit, study staff will administer the Female Follow-up Questionnaire and a study clinician will collect a double-headed vaginal swab. At 2 and 4-month visits, staff will provide condom counseling (per study arm), give 20 (or more if needed based on expected coital frequency) of the

assigned study condoms, and confirm the accuracy of the information on the Participant Contact Form. At the 6-month visit, all women will receive the standard condom, which is provided for free of charge per standard care.

Men will be asked to return at the 6-month visit to complete the Male Follow-up Questionnaire.

Female participants will be compensated at the end of the 2-month (110,000 VND; ~5 USD), 4-month (220,000 VND; ~10 USD), and 6-month visits (440,000 USD; ~20 USD) for their time and travel costs. Male participants will be compensated at the end of the 6-month visit (330,000 VND; ~15 USD).

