2. STUDY SUMMARY

This randomized controlled trial will test whether promoting the novel condom CSD500 (Futura Medical Developments; Surrey, UK) for improved sexual pleasure results in couples having less unprotected vaginal sex – measured with a biological marker of recent semen exposure – compared to the promotion of a standard condom for disease and pregnancy prevention. CSD500 contains an erectogenic drug and was developed to improve sexual pleasure by increasing penile firmness, size, and erection duration.

We will recruit eligible, monogamous, heterosexual couples at Thanh Hoa Provincial Centre of Reproductive Health in Vietnam to participate in a randomized controlled trial (RCT) of two balanced arms of approximately 250 couples each. At enrollment and at three follow-up visits scheduled at 2, 4 and 6 months after enrollment, we will provide condom counseling, will collect double-headed vaginal swabs to test for the semen biomarker, prostate-specific antigen (PSA), and will administer a questionnaire to the female participants on their demographics, sexual and condom-related attitudes and practices, including sexual pleasure and perceptions of partner's sexual pleasure. Although the intervention is directed to the women, couples will be enrolled to ensure that the male partners consent to CSD500 use. After enrollment, male participants will not participate in study visit activities, including data collection, until the time of their female partner's final 6-month visit. Because of the differences in counseling messages, participants and study staff at the site cannot be blinded to arm assignment.

Primary aims:

1. To evaluate whether CSD500 provided to improve sexual pleasure, as compared to the standard condom, results in less semen exposure among women in an established relationship
2. To evaluate the effects of CSD500 provision on men and women's reports of sexual pleasure compared to the standard condom
3. To identify correlates of semen exposure measured by PSA positivity

Study design: RCT with two arms: CSD500 for sexual pleasure or the standard condom currently provided for pregnancy and disease prevention

Study site: Thanh Hoa Provincial Centre of Reproductive Health

Data collection: Women: questionnaires and vaginal swabs for PSA testing at enrollment and the 2, 4, and 6-month visits
Men: questionnaires at enrollment and the 6-month visit

Sample size: ~500 couples with balanced assignment to the two study arms

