6.2 Eligibility criteria

The study will enroll approximately 500 couples with roughly equal distribution to the two study arms. Couples must speak Vietnamese to be eligible for study participation.

In addition, women must meet all of the following criteria at enrollment to be eligible:

- Be 18-45 years of age;
- Not currently using a modern contraceptive method other than condoms or intending to start using a modern contraceptive method other than condoms in the next 6 months;
- Willing to use the assigned study condoms as the sole method of contraception for the next six months;
- Not breastfeeding;
- Not known to be pregnant;
- Want to avoid pregnancy for at least the next six months; **and**
- Be in a monogamous relationship for at least the past six months with her current male partner.

Couples are ineligible for study participation if either person in the couple is known to be HIV-positive or has any of the following contraindications to CSD500 use (see Package Insert):

- History of low blood pressure or heart condition;
- Current use of medication for anemia, blood pressure, erectile dysfunction (man only), migraines, headaches or glaucoma;
- Inflamed or broken skin that the condom could come into contact with (man only); **or**
- Latex allergy or sensitivity.

Both the woman and her male partner need to be willing and able to consent to the study procedures, including the use of the assigned study condoms.

Our justification for excluding women who are known to be pregnant or already using a modern method of contraception other than condoms and couples in which either partner has a known HIV-infection is that these individuals might differ in unknown ways from others with respect to

their adherence to the promotion of condoms for avoiding semen exposure. Furthermore, individuals who are known to be HIV-positive typically receive more intensive safer sex counseling, and the scientific integrity of the study findings require that all participants receive standardized condom counseling according to their study arm.

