8.5 Condom counseling

Staff will provide standardized condom counseling on proper use of the assigned condom type to couples at enrollment and to the female participants at the follow-up visits (see Counseling Checklist: Control Arm and Counseling Checklist: Intervention Arm). Counseling for the two arms differs in the rationale given for condom use. Specifically, the intervention arm will receive counseling that briefly addresses condom's dual protection against pregnancy and HIV/STI but that otherwise emphasizes the potential for increased sexual pleasure with CSD500 use.

Counseling to this arm also will include CSD500-specific instructions, such as the need to briefly massage the gel inside the condom teat onto the penis head after donning the condom and to not use multiple condoms within a 24-hour period. In contrast, the control arm will receive standard counseling to use condoms for pregnancy and disease prevention without receiving any messages about the use of condoms for sexual pleasure.

Study staff will be trained with a formal curriculum (adapted from Pathfinder 2000) to counsel women on condom use. Training will address 1) key condom messages (per the intervention arm as described above); 2) mechanism of action and condom effectiveness; 3) factors that influence condom effectiveness; 4) indications and rationale for condom use; 5) counseling patients on correct condom use; and 6) correct condom storage procedures in service delivery settings. Only staff who demonstrate proficiency will provide condom counseling to study participants.

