16. ATTACHMENTS

1. Study timeline
2. Schedule of study procedures
3. Futura Max package insert
4. Futura Max packaging design
5. Recruitment Script
6. Counseling Checklist
 - Control Arm
 - Intervention Arm
7. Futura Max Information Sheet
8. Letters of support
 - [name] [name]
 - [name] [name], PhD
 - [name]
9. Data Safety and Monitoring Committee Charter
10. Data collection forms
 - Eligibility Assessment Form
 - Randomization Assignment Form
 - Vaginal Swab Collection Form
 - Female Enrollment Questionnaire
 - Male Enrollment Questionnaire
 - Female Follow-up Questionnaire
 - Male Follow-up Questionnaire
 - Study Discontinuation Form
 - Interim Visit Form
 - Adverse Event Form
11. Enrollment Consent Form
12. Annotated Enrollment Consent Form

Study timeline

Schedule of study procedures

Study procedure	Visit				
	Enroll- ment	2-month	4-month	6-month	Interim
Participant identification number (PIN) assigned	♀				
Eligibility Assessment Form	♀				
Enrollment Consent Form	♀				
Randomization Assignment Form	♀				
Female Enrollment Questionnaire	♀				
Male Enrollment Questionnaire	♂				
Condom counseling	♀ ^a	♀ ^a	♀ ^a	♀	
Condom provision	♀ ^a	♀ ^a	♀ ^a	♀	†
Provide Futura Max Information Sheet	♀ ^a	♀ ^a	♀ ^a		
Vaginal swab collection and Form	♀	♀	♀	♀	
Female Follow-up Questionnaire		♀	♀	♀	
Male Follow-up Questionnaire				♂	
Study Discontinuation Form	†	†	†	†	†
Interim Visit Form					†
Adverse Event Form	†	†	†	†	†
Obtain contact information	♀	♀	♀		
Participant compensation	♀	♀	♀	♀	

Procedure completed by couple (♀); woman only (♀); man only (♂); only if needed (†)

^aAccording to randomized arm assignment

VN CSD500 Study
Counseling Checklist: Control Arm

1. Greets patient respectfully.

- Assures privacy.
- Tries to put at ease if shy or embarrassed.

2. Asks what patient knows about condoms and about past experience with condoms.

- Corrects any myths or incorrect information.

3. Provides basic facts about condoms.

- Explains that condoms provide a barrier to 1) protect man and woman against spread of HIV and other sexually transmitted infections and 2) woman against pregnancy.
- Counsels talking with partner about using condoms.
- Asks if has any questions and answers them.

4. Provides specific instruction on how to correctly use and when to use condoms.

- Couple should use during every act of intercourse.
- Couple should not "test" condoms by blowing up or unrolling.
- Condom should be put on when penis is erect.

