- Corrects any technique errors.

8. Counsels patient on how to remove penis from vagina with condom intact and without spilling semen.

- Hold on to rim of condom when withdrawing.
- Be careful not to let semen spill into vagina when penis is flaccid.

9. Discusses use of lubricants and what not to use.

- Do not use any of these: petroleum-based products (e.g., Vaseline); mineral, vegetable, or cooking oil; baby oil; margarine or butter.

10. Advises to use a spermicide or water-based lubricant if one is needed.

11. Advises patient to dispose of condoms by burning, burying, or throwing in the latrine.

12. Repeats main condom messages to patient.

- Be sure to have condom on hand before you need it.
- Use a condom with every act of intercourse.
- Do not use a single condom more than once.
- Do not rely on condom if package is damaged, torn, outdated, dry, brittle or sticky.
- **Futura Max condoms are designed to make sex more fun for the couple. Futura Max condoms contain a special gel that makes the man's erection get harder and last longer. This can make sex more pleasurable for the couple.**

13. Provides patient with condoms for two months.

- Multiply patient's expected weekly coital frequency by 9. Give this number of condoms or, if this number is less than 20, give 20 condoms.
- Give 2 standard condoms to use in case the couple has sex more than once within 24 hours.

14. Instructs patient not to share study condoms with anyone but main partner.

- Do not share study condoms with family or friends.

15. Reassures patient that should return at any time for advice or more condoms.

[figure not shown]
VN CSD500 Study
Futura Max™ Information Sheet

Futura Max™ condoms are natural rubber latex condoms which contain Zanifil® gel. They have been shown to maximize hardness by stimulating blood flow within the penis. This can help prevent loss or partial loss of erection, ensuring an intense experience for both you and your partner.

How to use: Use a condom only once. Condoms used more than once are more likely to slip or break and not provide adequate protection. Infections can be passed on in bodily fluids present in the condom after use.

1. Tear open the foil and remove the condom. Be careful with sharp objects such as nails and jewelry. If the carton or foil is damaged, discard and use a condom from an undamaged package.

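### In the visible procedures staff check the CSD500 contraindications only at enrollment, and the 2- and 4-month resupply does not depend on any re-check

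*Combined protocol and SAP*

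**What the plan says.** Section 6.2 makes a couple ineligible if either partner "has any of the following contraindications to CSD500 use (see Package Insert"). One listed item is "Current use of medication for anemia, blood pressure, erectile dysfunction (man only), migraines, headaches or glaucoma". The others are a history of low blood pressure or a heart condition, inflamed or broken skin (man only), and latex allergy.

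Section 8.1 has staff establish eligibility on the Eligibility Assessment Form. The schedule of study procedures (section 16) marks that form at enrollment only.

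For follow-up, section 8.3 says: "At 2 and 4-month visits, staff will provide condom counseling (per study arm), give 20 (or more if needed based on expected coital frequency"). The other steps at those visits are the female questionnaire, the swab and confirmation of contact details. At month 6 the product changes: "At the 6-month visit, all women will receive the standard condom".

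The man is largely out of view. Section 2 says that "male participants will not participate in study visit activities, including data collection, until the time of their female partner's final 6-month visit", and section 8.5 directs counseling "to couples at enrollment and to the female participants at the follow-up visits".

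Between scheduled visits, item 15 of the intervention checklist reads "Reassures patient that should return at any time for advice or more condoms". The schedule row "Condom provision" carries an if-needed mark in the interim column.

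**The concern.** The contraindications differ in kind from the other exclusions in 6.2. The plan justifies excluding pregnant women, users of other modern methods and people with HIV because their adherence or counseling might differ. The contraindications are tied to the package insert of a product containing glyceryl trinitrate. They therefore matter for as long as the product is used, which is six months, and not only on the day of entry.

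A single check at entry cannot detect a medicine started later. The main case is a listed medicine taken without symptoms, such as a blood-pressure, glaucoma or erectile-dysfunction drug. The man is the harder partner to cover: the erectile-dysfunction item applies to him alone, and staff are not scheduled to see him at either resupply. A new contraindication is also plausible for an ordinary reason. Section 12.1 lists headache as an expected adverse event, and headache medicine is on the 6.2 list.

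What is at stake is the safety of intervention-arm participants, not the validity of the primary analysis.

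**Working it through.** The plan gives no figure to reproduce. The check compares the sections, followed by a simple count.

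**Where a check could appear**

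- Section 8.3, months 2 and 4: resupply is listed among the visit steps with no precondition.
- Schedule: the Eligibility Assessment Form is not repeated after enrollment, and no other row names contraindications or medicines.
- Intervention checklist: all 15 items are in the text. They cover the 24-hour limit, applying the gel, lubricants and quantities. None asks or warns about medicines or conditions. Item 13 sets the number of condoms and nothing else.
- Section 13.3: users stop if symptoms occur. This misses a medicine taken without symptoms.
- Section 12.1: a new diagnosis may count as an adverse event and so reach the Site Investigator. Starting a medicine is not in itself an untoward event.
- Section 8.9: staff may discontinue a participant, but only if they know of a reason.
- Section 13.8: the DSMC reviews accumulated data, not individual dispensing.

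None of these is a staff check before CSD500 is handed out.

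**Share of supply issued without a described re-check**

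CSD500 is supplied at months 0, 2 and 4, at least 20 condoms each time (item 13; section 8.3). For a couple attending all three visits, the minimum total is 3 × 20 = 60. The minimum after month 0 is 2 × 20 = 40, or two thirds.

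**Scheduled resupply occasions**

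Inputs from section 9.1: about 250 couples per arm, and 10% not returning after enrollment. Couples returning: 250 × 0.90 = 225. Section 9.1 words the remaining attrition in two ways:

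| Reading | Formula | Result |
|---|---|---|
| Each follow-up visit is missed with probability 25% (closing text) | 225 × 2 × 0.75 | 337.5, about 338 |
| A quarter of couples miss one visit (figure footnote), taken as equally likely to be any of the three | 225 × (2 − 0.25 × 2/3) | 412.5, about 413 |

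Month 6 is left out because standard condoms are given then. Interim supplies cannot be counted. No rate of new contraindications is assumed, because the documents give none.

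**The case against.** The strongest reply is that this rests on silence. The Female Follow-up Questionnaire is administered at both resupply visits and its items are not available. Nor are the Interim Visit Form, the Adverse Event Form, the package insert or most of the Information Sheet. Any of these may ask or warn about new medicines, and protocols often leave such wording to forms. This stands as a limit: the finding is that no check is described, not that none exists. It does not remove the point, because even a questionnaire that asks would not make dispensing depend on the answer unless the procedure says so.

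Second, other safeguards exist. Both partners are screened and counselled at entry. The intervention arm receives the Information Sheet again at months 2 and 4. A clinician takes the woman's swab at each follow-up, and section 8.4 invites any participant, men included, to return with a study-related problem. For a product that section 3 describes as approved over the counter in 27 European nations, reliance on user information is defensible. This supports a low severity. These measures still rely on the participant to raise the matter.

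Third, a reader might infer from item 15 that CSD500 is routinely resupplied at interim visits. The documents do not establish that. The interim mark in the schedule lacks the footnote tying supply to the assigned arm, section 8.4 does not mention resupply, and item 15 does not name the condom. Interim CSD500 supply is an inference.

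Fourth, re-asking works worst where the gap is widest, since the woman may not know of her partner's medicines. That is correct, and it is why the fix also includes an instruction to both partners.

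**Conclusion.** The point holds as a low-severity participant-safety matter. In the visible procedures staff check the 6.2 contraindications once, and the 2- and 4-month resupply is not conditional on a re-check for either partner. Followed as written, staff would resupply a couple who had come to fail the medicine screen.

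This rests on two assumptions: that contraindications to use apply throughout use, and that the unseen forms do not already require staff to act on a new medicine before dispensing. If the questionnaire does ask, what remains is a missing link between the answer and the supply.

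Two stronger readings are not supported. A reader might take 338 to 413 as the number of couples exposed to risk. It counts scheduled resupply occasions, and the number with a new contraindication may be small and cannot be derived. A reader might also suspect bias in the primary result. Nothing in the documents shows that, and the intent-to-treat PSA comparison is not called into question. Section 13.3 rates the study as no more than minimal risk, and nothing here overturns that rating.

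**What to change.** Add one item to the intervention-arm checklist, placed before condoms are handed out, and refer to it in section 8.3 and the schedule. It would apply at month 2, month 4 and any interim visit at which CSD500 is supplied:

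1. Staff re-ask the 6.2 medicine and condition items for both partners. If the Female Follow-up Questionnaire already asks, staff review those answers before dispensing.
2. Any positive answer goes to the study clinician before CSD500 is given.
3. If the contraindication is confirmed, the couple receives standard condoms, and visits and swabs continue under intent-to-treat. The intervention arm already gets two standard condoms under item 13, so the fallback is familiar.
4. Both partners are told at enrollment, when they are counselled together, to stop CSD500 and use a standard condom if either starts a listed medicine. The woman is reminded at each resupply. This reaches the man more directly and covers medicines started between visits.

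Control couples need not be asked, since the questions would serve no safety purpose for them.

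The cost is a few minutes per visit, using existing items at existing visits, with no extra visits or staff. Two downsides remain. The woman's report on the man is imperfect. CSD500 exposure would also fall by an unknown amount, because headache is an expected adverse event and headache medicine is on the list.

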8.4 Interim visits

We will instruct participants to return to the clinic at any time for any study-related problem. Also, study staff may request that participants attend interim visits to follow-up on adverse events (AEs). All procedures at interim visits will be documented on the Adverse Event Form.

8.5 Condom counseling

Staff will provide standardized condom counseling on proper use of the assigned condom type to couples at enrollment and to the female participants at the follow-up visits (see Counseling Checklist: Control Arm and Counseling Checklist: Intervention Arm). Counseling for the two arms differs in the rationale given for condom use. Specifically, the intervention arm will receive counseling that briefly addresses condom's dual protection against pregnancy and HIV/STI but that otherwise emphasizes the potential for increased sexual pleasure with CSD500 use.

Counseling to this arm also will include CSD500-specific instructions, such as the need to briefly massage the gel inside the condom teat onto the penis head after donning the condom and to not use multiple condoms within a 24-hour period. In contrast, the control arm will receive standard counseling to use condoms for pregnancy and disease prevention without receiving any messages about the use of condoms for sexual pleasure.

Study staff will be trained with a formal curriculum (adapted from Pathfinder 2000) to counsel women on condom use. Training will address 1) key condom messages (per the intervention arm as described above); 2) mechanism of action and condom effectiveness; 3) factors that influence condom effectiveness; 4) indications and rationale for condom use; 5) counseling patients on correct condom use; and 6) correct condom storage procedures in service delivery settings. Only staff who demonstrate proficiency will provide condom counseling to study participants.

8.6 Specimen collection and testing

Trained clinicians will collect a vaginal fluid specimen (using a 1-mL, rayon-tipped double-headed swab) from each participant at each of the four scheduled study visits. Swabs will be stored onsite at -70°C following collection until their shipment in batches on dry ice to the UNC laboratory, where one of the double-headed swabs will be processed and tested in batches for total PSA (Architect Total PSA; Abbott Diagnostics, Abbott Park, IL) by trained laboratory personnel following established procedures (Gallo 2013a). The second of the double-headed swabs may be used for quality assurance testing during the study.

